### **Protocol Page 27, Section 12, Table 5 Schedule of Assessments and Procedures:**

*Add “Taste evaluationh” to Table 5 with the following footnote:*

*h. Taste evaluation will be conducted immediately after dosing and 5 minutes after administration to determine any after taste.*

Protocol Number Pa-824-CL-011

Protocol Clarification Letter 2

### **Protocol Clarification Letter 3**

TB Alliance, Protocol Pa-824-CL-011, An Open-label, Randomized, Four-period, Crossover Study in Two Panels of Healthy Adult Participants to Assess the Relative Bioavailability, Food Effect, and Dose-dependence of Single-Dose Immediate-Release and Single-dose Dispersible Formulations of Pretomanid

The purpose of this letter is to update the contact information for serious adverse event (SAE) reporting. The section of protocol version 1.0 dated 06 Dec 2019 affected by this change is indicated below.

## SAP Amendments Before Database Lock

Version	Issue Date	Section	Revision / Addition	Rationale
	Not Applicable			

QMD Ref: Worldwide-TMP-ST-006-4.0 Effective: 12Aug2019	Governing QMD: Worldwide-SOP-ST-001
Confidentiality Statement	
This document is the property of Worldwide Clinical Trials Inc. and may not be duplicated, copied, altered or removed from company without prior approval from Worldwide Quality Assurance or in compliance with Worldwide Standard Operating Procedures.	

Worldwide Clinical Trials Controlled Quality Management Document		
 WORLDWIDE CLINICAL TRIALS	Sponsor: Protocol Number:	TB Alliance Pa-824-CL-011
STATISTICAL ANALYSIS PLAN – PHASE 1		

## 1 INTRODUCTION

This document details the planned statistical analyses for TB Alliance, protocol “Pa-824-CL-011” study titled “An Open-label, Randomized, Four-period Crossover Study in Two Panels of Healthy Adult Participants to Assess the Relative Bioavailability, Food Effect, and Dose-dependence of Single-Dose Immediate-Release and Single-dose Dispersible Formulations of Pretomanid”. The proposed analyses are based on the contents of the final version of the protocol (dated 06-Dec-2019).

This is a single-dose, open-label, randomized, four-period, four-treatment, crossover study in healthy adult subjects. Each panel of 24 subjects will be randomized according to the same 4-sequence, 4-period Williams design, in which each participant will receive four single-dose treatments. Subjects in Panel 1 will receive all treatments after consuming an FDA standard high-fat, high-calorie breakfast following an overnight fast of at least 10 hours. Subjects in Panel 2 will receive all treatments directly following an overnight fast of at least 10 hours. The two panels will be investigated concurrently. The maximum duration of the study from screening to study exit will be approximately 54 days.

## 2 STUDY OBJECTIVES

### 2.1 Primary Objective

The primary objective of the study is to assess the relative bioavailability of the single-dose dispersible formulation intended for pediatric treatment, using the 200-mg single-dose immediate-release formulation as the reference.

### 2.2 Secondary Objectives

The secondary objectives of the study are as follows:

- To determine the food effect for each of the formulations.
- To assess the effect of dose on the bioavailability of the dispersible pediatric formulation under fed and fasted conditions.
- To evaluate the taste perception of the dispersible pediatric formulation under fed and fasted conditions.
- To evaluate the short-term safety and tolerability for each of the formulations under fed and fasted conditions.

QMD Ref: Worldwide-TMP-ST-006-4.0 Effective: 12Aug2019	Governing QMD: Worldwide-SOP-ST-001
Confidentiality Statement This document is the property of Worldwide Clinical Trials Inc. and may not be duplicated, copied, altered or removed from company without prior approval from Worldwide Quality Assurance or in compliance with Worldwide Standard Operating Procedures.	

Worldwide Clinical Trials Controlled Quality Management Document		
 WORLDWIDE CLINICAL TRIALS	Sponsor: Protocol Number:	TB Alliance Pa-824-CL-011
STATISTICAL ANALYSIS PLAN – PHASE 1		

### **3 ENDPOINTS**

#### **3.1 Safety Endpoints**

Safety assessments will include physical examinations, vital sign measurements, clinical laboratory evaluations, electrocardiograms (ECGs), and reported or observed adverse events (AEs). Subjects will be monitored continuously for any AEs from the signing of the informed consent through the end of the study.

#### **3.2 Pharmacokinetic Endpoints**

Full pharmacokinetic (PK) profiles of pretomanid will be determined up to 96 hours after each intake of pretomanid. Blood samples for analysis of pretomanid concentrations will be drawn just before drug intake (pre-dose), and at 0.5, 1, 2, 3, 4, 6, 8, 12, 16, 24, 36, 48, 72, and 96 hours post dose (15 samples per dose).

Primary PK measures include  $T_{max}$ ,  $C_{max}$ ,  $AUC_{0-t}$ , and  $AUC_{0-inf}$ . Secondary PK measures include the ratio of  $AUC_{0-t}$  to  $AUC_{0-inf}$ ,  $T_{1/2}$ ,  $Kel$ ,  $Cl/F$  and  $Vd/F$ .

### **4 SAMPLE SIZE**

Two panels of healthy male and female subjects (24 subjects per panel) will be dosed in this study. The sample size is not based on statistical considerations. The number of subjects planned for enrollment is considered sufficient to achieve the study objectives.

### **5 RANDOMIZATION**

This is an open-label study without treatment blinding. Subjects will be randomly allocated to a panel by clinic staff, and the two panels will be investigated concurrently. Subjects in each panel (Panel 1 = Fed, Panel 2 = Fasted) will be randomized to a treatment sequence based on a 4-sequence, 4-period Williams design prepared by the independent statistician.

QMD Ref: Worldwide-TMP-ST-006-4.0 Effective: 12Aug2019	Governing QMD: Worldwide-SOP-ST-001
Confidentiality Statement	
This document is the property of Worldwide Clinical Trials Inc. and may not be duplicated, copied, altered or removed from company without prior approval from Worldwide Quality Assurance or in compliance with Worldwide Standard Operating Procedures.	

Worldwide Clinical Trials Controlled Quality Management Document			
 WORLDWIDE CLINICAL TRIALS	Sponsor:	TB Alliance	
	Protocol Number:	Pa-824-CL-011	
STATISTICAL ANALYSIS PLAN – PHASE 1			

**Table 1: Treatment Schedule**

Sequence (n=24 subjects per panel)	Treatment Periods			
	Period 1	Period 2	Period 3	Period 4
ABCD	A	B	C	D
BDAC	B	D	A	C
CADB	C	A	D	B
DCBA	D	C	B	A

Treatment A (reference) = 200 mg given as a single 200 mg tablet (using the immediate release formulation), orally administered.

Treatment B (test) = 200 mg given as four 50-mg tablets (using the dispersible pediatric formulation), orally administered.

Treatment C (test) = single 50-mg dispersible tablet, orally administered.

Treatment D (test) = single 10-mg dispersible tablet, orally administered.

## 6 PLANNED ANALYSES

No statistical analysis plan (SAP) prepared in advance of the data can be absolutely definitive and the final Clinical Study Report (CSR) may contain additional tables or statistical tests if warranted by the data obtained. The justification for any such additional analyses will be fully documented in the final CSR.

### 6.1 Analysis Sets

Subjects excluded from the analysis sets and the reason for their exclusion will be listed in [Appendix 16.2](#) of the CSR.

#### 6.1.1 Randomized Set

The Randomized Set includes all subjects to whom a treatment was randomly assigned.

#### 6.1.2 Safety Analysis Set

The Safety Analysis Set includes all subjects who received any dose of study drug.

#### 6.1.3 Pharmacokinetic Analysis Set

All evaluable subjects completing at least one treatment period will be included in the PK analysis set.

QMD Ref: Worldwide-TMP-ST-006-4.0 Effective: 12Aug2019	Governing QMD: Worldwide-SOP-ST-001
Confidentiality Statement	

This document is the property of Worldwide Clinical Trials Inc. and may not be duplicated, copied, altered or removed from company without prior approval from Worldwide Quality Assurance or in compliance with Worldwide Standard Operating Procedures.

Worldwide Clinical Trials Controlled Quality Management Document		
 WORLDWIDE CLINICAL TRIALS	Sponsor: Protocol Number:	TB Alliance Pa-824-CL-011
STATISTICAL ANALYSIS PLAN – PHASE 1		

## 6.2 Derived Data

This section describes the derivations required for statistical analysis. Unless otherwise stated, variables derived in the source data will not be re-calculated.

### 6.2.1 Race

Where more than one race category has been selected for a subject, these race categories will be combined into a single category labeled “Multiple Race” in the summary tables. The listings will reflect the original selected categories.

### 6.2.2 Baseline

For variables that will be summarized by treatment, the baseline for each period is defined as the last non-missing value (either scheduled, unscheduled or repeat) that is collected before dosing, but after check-in for the relevant period.

For variables that will be summarized overall, baseline is defined as the last non-missing value (either scheduled, unscheduled or repeat) that is collected before the subject receives the first dose of study drug.

### 6.2.3 Early Terminations Assessments

Early withdrawal (EW) assessments will be tabulated with End of Study (EOS).

### 6.2.4 Duration / Study Day / Time

Study day will be calculated as the number of days from first dose of study drug.

- date of event – date of first dose of study drug + 1, for events on or after first dose
- date of event – date of first dose of study drug, for events before first dose.

### 6.2.5 Conventions for Missing and Partial Dates

It is not expected that there will be any missing dates, however in the rare case that an Adverse Event (AE) start date or time is missing and it is unclear whether the AE is treatment emergent or not then a conservative approach will be taken and it will be assumed that the AE occurred after first dosing.

All dates presented in the individual subject listings will be as recorded on the Electronic Case Report Form (eCRF).

QMD Ref: Worldwide-TMP-ST-006-4.0 Effective: 12Aug2019	Governing QMD: Worldwide-SOP-ST-001
Confidentiality Statement This document is the property of Worldwide Clinical Trials Inc. and may not be duplicated, copied, altered or removed from company without prior approval from Worldwide Quality Assurance or in compliance with Worldwide Standard Operating Procedures.	

Worldwide Clinical Trials Controlled Quality Management Document		
 WORLDWIDE CLINICAL TRIALS	Sponsor: Protocol Number:	TB Alliance Pa-824-CL-011
STATISTICAL ANALYSIS PLAN – PHASE 1		

## 6.2.6 Inexact Values

In the case where a safety laboratory variable is recorded as “> x”, “ $\geq$  x”, “ $<$  x” or “ $\leq$  x”, a value of x will be taken for analysis purposes.

## 6.2.7 Unscheduled Visits

Only scheduled post-baseline assessments will be tabulated. Post-baseline repeat / unscheduled assessments will not be summarized but will be listed in the relevant appendices to the CSR.

## 6.2.8 PK Parameters

### 6.2.8.1 Concentration-Time Data

Blood samples for analysis of pretomanid concentrations for each panel (Panel 1=Fed; Panel 2=Fasted) will be drawn just before drug intake (pre-dose), and at 0.5, 1, 2, 3, 4, 6, 8, 12, 16, 24, 36, 48, 72, and 96 hours post dose (15 samples per dose).

Concentration-time data will be tabulated by panel, treatment, and nominal time using descriptive statistics including: sample size (n), arithmetic mean (mean), standard deviation (SD), percentage coefficient of variation (% CV), geometric mean, median, minimum (min), and maximum (max). For presentation of the individual data and summary statistics, concentrations below the limit of quantitation (BLQ) will be set to zero. Geometric means will be presented as NC (not calculated) if BLQ values are present in the concentration-time dataset.

Individual subject and mean plasma concentration-time data will be presented graphically on linear and semi-logarithmic scales by panel. Mean data will be plotted using nominal sample times, and individual data will be plotted using actual times.

### 6.2.8.2 PK Parameters

Concentration-time data for pretomanid will be analyzed by noncompartmental methods using Phoenix™ WinNonlin® (Version 8.1, Certara, L.P.) in conjunction with the internet-accessible implementation of Pharsight® Knowledgebase Server™ (PKSO; Version 4.0.4, Certara, L.P.).

During the pharmacokinetic analysis, concentrations below the limit of quantitation (BLQ) up to the time of the first quantifiable concentration will be treated as zero. Embedded (values between 2 quantifiable concentrations) and terminal BLQ concentrations will be treated as “missing”. Actual sample times relative to the time of dose administration will be used in the PK analysis. If actual times are missing, nominal times may be used.

QMD Ref: Worldwide-TMP-ST-006-4.0 Effective: 12Aug2019	Governing QMD: Worldwide-SOP-ST-001
Confidentiality Statement	
This document is the property of Worldwide Clinical Trials Inc. and may not be duplicated, copied, altered or removed from company without prior approval from Worldwide Quality Assurance or in compliance with Worldwide Standard Operating Procedures.	

Worldwide Clinical Trials Controlled Quality Management Document		
 WORLDWIDE CLINICAL TRIALS	Sponsor: Protocol Number:	TB Alliance Pa-824-CL-011
STATISTICAL ANALYSIS PLAN – PHASE 1		

The following PK parameters will be calculated for pretomanid for each panel:

Parameter	Definition
$C_{max}$	Maximum plasma concentration, determined directly from individual concentration-time- data
$T_{max}$	Time of the maximum plasma concentrations
$C_{last}$	Last quantifiable plasma concentration determined directly from individual concentration-time data
$T_{last}$	Time of the last quantifiable plasma concentration
$AUC_{0-t}$	Area under the plasma concentration-time curve from time-zero to the time of the last quantifiable concentration ( $C_{last}$ ), as calculated by the linear trapezoidal rule
$AUC_{0-inf}$	Area under the plasma concentration-time curve from the time of dosing extrapolated to infinity, calculated as: $AUC_{0-inf} = AUC_{0-t} + C_{last}/\lambda_z$ , where $\lambda_z$ is the apparent terminal elimination rate constant calculated by linear regression of the terminal linear portion of the log concentration versus time curve
$AUC_{Extrap}$	The percentage of $AUC_{0-inf}$ based on extrapolation, calculated as: $[1 - (AUC_{0-t}/AUC_{0-inf})] * 100$
$\lambda_z$ ( $K_{el}$ , Lambda z)	The apparent elimination rate constant $\lambda_z$ will be calculated as the negative of the slope of the linear regression through the terminal log-linear segment of the plasma concentration-time curve (additional criteria are summarized below)
$T_{1/2}$	The observed terminal elimination half-life, calculated as: $T_{1/2} = \ln(2)/\lambda_z$

QMD Ref: Worldwide-TMP-ST-006-4.0 Effective: 12Aug2019	Governing QMD: Worldwide-SOP-ST-001
Confidentiality Statement	

This document is the property of Worldwide Clinical Trials Inc. and may not be duplicated, copied, altered or removed from company without prior approval from Worldwide Quality Assurance or in compliance with Worldwide Standard Operating Procedures.

Worldwide Clinical Trials Controlled Quality Management Document		
 WORLDWIDE CLINICAL TRIALS	Sponsor: Protocol Number:	TB Alliance Pa-824-CL-011
STATISTICAL ANALYSIS PLAN – PHASE 1		

Parameter	Definition
CL/F	The apparent total plasma clearance after an oral dose, calculated as: CL/F=Dose/AUC 0-inf , where F is the bioavailability,
V z /F	The apparent volume of distribution after an oral dose, calculated as: V z /F=Dose/(AUC 0-inf × λ z ), where F is the bioavailability,

#### Lambda-z (λz) Acceptance Criteria

The following criteria will be used to report lambda-z and related parameters:

- At least 3 quantifiable concentration-time points should be used in the regression
- Cmax or data prior to Cmax should not be included in the regression
- Adjusted R^2 should be ≥ 0.8000

If these acceptance criteria are not met, lambda-z and descriptive parameters such as the time range for the regression, adjusted R^2, etc. will be retained in a parameter listing for informational purposes. Lambda-z will be excluded from summary statistics and from subsequent PK calculations; parameters calculated using lambda-z (e.g. t1/2, AUC0-inf, CL/F, and Vz/F) will be reported as ND (not determinable).

If lambda-z acceptance criteria are met and AUC0-inf is estimable, the following criteria are used to report AUC0-inf:

- The percentage of AUC0-inf based on extrapolation should be <30.0%.

If the percentage of AUC0-inf based on extrapolation is 30.0% or greater, AUC0-inf and AUCExtrap will be retained in a PK parameter listing for informational purposes; these parameters will be excluded from summary statistics, subsequent PK calculations (e.g. CL/F, Vz/F), and statistical analysis (e.g. ANOVA).

PK parameters will be summarized separately for each panel by treatment using the following descriptive statistics: n, mean, SD, median, min, max, CV%, geometric mean, and geometric mean CV%.

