## **8.2 Pharmacokinetic and Statistical Analyses**

Primary pharmacokinetic measures include  $T_{max}$ ,  $C_{max}$ ,  $AUC_{0-t}$ , and  $AUC_{0-inf}$ . Secondary pharmacokinetic measures include the ratio of  $AUC_{0-t}$  to  $AUC_{0-inf}$ ,  $T_{1/2}$ ,  $K_{el}$ ,  $Cl/F$  and  $V_d/F$ .

All evaluable subjects completing at least one treatment period will be included in the pharmacokinetic analysis.

Descriptive statistics will be used to summarize pretomanid plasma concentrations at each sampling time point and for derived plasma PK parameters, as applicable. Statistics include sample size (n), mean, SD, percentage coefficient of variation (%CV), geometric mean, median, minimum, and maximum.

For each participant, pretomanid plasma concentration-time data will be graphically presented. Similarly, graphs of the mean plasma concentration-time profiles and overlay graphs with combined individual plasma concentration-time profiles will be produced. Additionally, pharmacokinetic parameters may be explored graphically.

The bioavailability of 4 x 50 mg dispersible tablets relative to the 200-mg reference tablet will be determined separately for each panel using a mixed model with the log transformed PK parameter ( $C_{max}$ ,  $AUC_{0-t}$ , and  $AUC_{0-inf}$ ) as response variable; sequence, period, and treatment as fixed effects; and participant as random effect.

The effect of dose on the relative bioavailability of the dispersible tablet will be determined separately for each panel using the same model as above.

The effect of food on the relative bioavailability of pretomanid will be determined comparing, across panels, each formulation and dose taken after eating breakfast versus

Protocol Pa-824-CL-011 V1.0

the same formulation and dose taken in fasted conditions using a mixed model with the log transformed PK parameter as response variable; panel, sequence, period, treatment, and panel-by-treatment interaction as fixed effects; and participant as random effect.

The  $T_{max}$  of pretomanid for each of the formulations will be descriptively compared.

Other statistical models and/or population pharmacokinetic modelling may also be used for further data interpretation.

Pharmacokinetic calculations will be performed using appropriate software.

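### The SAP drops extrapolated percentages of 30% or more from the summary of the extrapolated percentage itself, so the descriptive summary of a secondary PK measure is truncated by construction (minor)

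*SAP*

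**What the plan says.** Protocol 8.2 names the ratio AUC0-t/AUC0-inf as a secondary measure ("Secondary pharmacokinetic measures include the ratio of" that pair), and SAP 3.2 repeats this ("Secondary PK measures include the ratio of" the two areas). The parameter table in SAP 6.2.8.2 has no row for the ratio. It has AUCExtrap, the percentage of AUC0-inf that is extrapolated, defined as one minus that ratio, times 100.

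The acceptance criteria in the same section work in two steps. If lambda-z fails its criteria, every parameter that uses it (half-life, AUC0-inf, CL/F, Vz/F) is reported as not determinable. If lambda-z is accepted, a second limit applies: the percentage "based on extrapolation should be <30.0"%. At 30.0% or above, the SAP names both AUC0-inf and AUCExtrap. They "will be retained in a PK parameter listing for informational purposes", and "these parameters will be excluded from summary statistics, subsequent PK calculations" and statistical analysis. The section then states: "PK parameters will be summarized separately for each panel by treatment using the following descriptive statistics: n, mean, SD, median, min, max, CV"%, followed by the geometric statistics.

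The protocol sets no extrapolation limit. Its synopsis (criteria for evaluation, pharmacokinetics) has the summaries cover every subject who completed the period. SAP section 7 declares no change to the protocol's planned analyses.

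**The concern.** Withholding AUC0-inf, CL/F and Vz/F when much of the area is extrapolated is sensible, because those estimates are then unreliable. AUCExtrap plays a different part: it is the diagnostic that shows the unreliability. Removing its high values from its own summary removes the part of the distribution that the summary exists to show.

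The measure tells a reader whether sampling to 96 h, with this assay, captured the profile. One sampling schedule serves doses from 10 to 200 mg. Other things equal, the 10-mg profiles would fall below the assay limit first. The summary row that most directly answers the coverage question would then look acceptable in every arm, whatever the data. What is at stake is a fair description of a stated secondary measure, not the comparison of formulations.

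**Working it through.** **Inputs from the documents.** The limit is 30.0% or greater (SAP 6.2.8.2, acceptance criteria). The definition is AUCExtrap = [1 − (AUC0-t/AUC0-inf)] × 100 (SAP 6.2.8.2, parameter table). There are 24 subjects per panel (SAP 4), and the last sample is at 96 h (SAP 3.2). Half-life and assay limit are not given.

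**Step 1: the limit expressed as a ratio.** AUCExtrap ≥ 30.0 is the same as AUC0-t/AUC0-inf ≤ 0.70.

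- Ratio 0.7001: (1 − 0.7001) × 100 = 29.99%, summarised.
- Ratio 0.70: 30.0%, excluded.
- Ratio 0.69: 31.0%, excluded.

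Before rounding, the summarised maximum of AUCExtrap is therefore below 30% and the summarised ratio is above 0.70 for any data set.

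**Step 2: what the truncation does to the mean.** The true distribution is unknown, so these are assumed cases. With AUCExtrap beta-distributed with mean m and SD s (as fractions), put k = m(1 − m)/s² − 1, a = mk and b = (1 − m)k. The excluded share is 1 − F(0.30; a, b), and the mean of what is kept is m × F(0.30; a+1, b)/F(0.30; a, b). For m = 0.20 and s = 0.10: k = 0.16/0.01 − 1 = 15, a = 3, b = 12.

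| Assumed AUCExtrap, mean (SD) | Excluded | Expected n of 24 | True mean ratio | Summarised mean ratio |
|---|---|---|---|---|
| 10% (5) | 0.2% | 24.0 | 0.90 | 0.90 |
| 20% (10) | 16% | 20.1 | 0.80 | 0.83 |
| 28% (10) | 40% | 14.5 | 0.72 | 0.79 |
| 35% (12) | 64% | 8.7 | 0.65 | 0.77 |

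Log-normal distributions with CV 40 to 50% give the same picture on the percentage scale:

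- Median 15%: 4 to 7% of profiles lost; summarised mean 15.2 to 15.4% against a true 16.2 to 16.8%.
- Median 20%: 15 to 20% lost; 18.1 to 18.9% against 21.5 to 22.3%.
- Median 30%: half lost; 21 to 23% against 32 to 33%.

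**Step 3: when the limit would be reached.** For a mono-exponential curve the extrapolated fraction is about 2^(−Tlast/T½), so 30% needs T½ = Tlast × ln 2/(−ln 0.30). For Tlast of 96, 48 and 24 h that is 55.3, 27.6 and 13.8 h. The documents do not say which of these applies, so how often the rule would bite cannot be worked out from them.

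**Step 4: what the report still shows.** A lambda-z failure removes T½ and AUC0-inf together. The 30% rule removes AUC0-inf but leaves T½. Hence n(T½) − n(AUC0-inf), by treatment and panel, is the number of profiles dropped by the 30% rule.

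**The case against.** The strongest reply is that the report as a whole conceals nothing. The same sentence keeps the excluded values in a listing, and SAP 6.3 says all data will be listed. Step 4 shows that the count lost to the rule can be recovered from the reported n. Tlast and Clast are calculated parameters that the rule does not touch. Concentrations are tabulated at each nominal time, and individual semi-logarithmic profiles are planned. A short quantifiable window at 10 mg would show in all of these.

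All of this stands, and it rules out two stronger readings. A reader might infer that the plan can never reveal a coverage failure; that is true of the summary of this one measure, not of the report. A reader might also infer that the plan hides selective loss of AUC0-inf by dose or panel; the reported n values contradict that.

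The reply also notes that the more extreme cases are hard to reach. If samples are quantifiable to 96 h, 30% extrapolation needs a half-life near 55 h, which would leave 2^(−168/55.3) = 12% after the 7-day washout. That sits badly with the SAP's own 5% predose limit. This is fair for late Tlast, but it does not cover an earlier Tlast, where shorter half-lives suffice.

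Finally, the measure is descriptive and no decision rule rests on it. That limits the severity. It does not justify truncating a named secondary measure on its own value: the listing gives the individual values, but the mean, maximum and SD in the table remain those of a selected subset.

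**Conclusion.** The point holds as a minor reporting defect. The truncation follows from the SAP's wording and its own definition, with no assumption about the data. If any profile reaches 30%, the summary of AUCExtrap is biased toward good coverage.

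The size rests on distributions that the documents do not supply. Under the beta cases it runs from no visible change in the mean ratio (true 0.90) to 0.77 reported against 0.65. If no profile reaches 30%, the effect is nil.

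Nothing modelled is affected. The B-versus-A comparison uses Cmax, AUC0-t and AUC0-inf, and AUCExtrap enters none of the models. Whether AUC0-inf itself should be dropped at 30% is a separate matter, and it is not disputed here.

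**What to change.** In the acceptance criteria of SAP 6.2.8.2, keep the 30% rule for AUC0-inf, CL/F and Vz/F, and delete AUCExtrap from the exclusion from summary statistics. Summarise AUCExtrap, or the ratio AUC0-t/AUC0-inf, for every profile with an accepted lambda-z. Optionally, add to Table 14.4.2 the number of profiles at 30% or more by treatment and panel, so that the reader need not derive it from two values of n.

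The cost is one SAP sentence, with one further table row if the count is added. The summary may look slightly less favourable. The n for AUC0-inf, CL/F and Vz/F will still differ from the n for half-life when the rule applies. That is expected, and a footnote can say so.
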